7.4. Physical Examination

Brief physical examination data will be collected at Screening, Baseline, Week 12 and 24. A listing of all physical exam results for subjects with at least one abnormal result will be produced.

7.5. Post-Void Residual (PVR) Urine Volume

PVR urine volume data will be summarized at Baseline and every visit, including change from baseline for post-baseline visits. Least squares mean estimates and 95% CIs as described in section 4.2.2 will be presented from an ANCOVA model including terms for treatment and baseline parameter value.

Categorical summaries of PVR at the following categories: < 100 mL, ≥ 100 and < 200 mL, ≥ 200 and < 300 mL, ≥ 300 mL will be presented. Line plots of least squares means change from baseline and 95% CIs by visit and treatment will be presented. All PVR data will be listed.

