2.4.2. Potential Risks

The initial clinical program for vibegron in the treatment of OAB included subjects of both sexes. The Phase 3 program in OAB (RVT-901-3003 and RVT-901-3004) included approximately 15% males, contributing safety data comprising 217 men in addition to those enrolled in Study URO-901-3005. More detailed information about the known and expected benefits and risks from the study and reasonably expected AEs of vibegron may be found in the Investigator's Brochure.

Based on aggregate preclinical, clinical pharmacology, and Phase 2 and 3 studies, AEs of special interest (AESIs) were predefined for specific evaluations in vibegron clinical studies as follows:

- Potential major cardiovascular events
- Hypertension
- AEs suggestive of orthostatic hypotension
- AEs suggestive of cystitis or urinary tract infection
- Elevated aspartate transaminase (AST) or alanine transaminase (ALT) laboratory value requiring that the study drug be temporarily withheld or permanently discontinued
- Neoplasm

In addition, the risk for increases in post void residual urine volume and urinary volume will be closely monitored for post-void retention during the study. The study's enrollment criteria will exclude men with PVR volume ≥ 100 mL at screening and at baseline and those with maximum urinary flow (Qmax) less than 5 mL/second. Post-void residual urine volume will be assessed throughout the study, and subjects with a single PVR volume of ≥ 300 mL or an AE of urinary retention will be withdrawn.

Prespecified definitions of urinary retention and other AESIs are provided in the Adverse Event of Special Interest section ([Section 8.4.6](#)).

3. Objectives and Endpoints

Objectives	Endpoints
Primary Efficacy 
 To assess the efficacy of vibegron compared with placebo in men with OAB symptoms on pharmacological therapy for BPH as defined by micturition and urgency episodes 	Primary Efficacy 
 CFB at Week 12 in the average number of micturition episodes per day CFB at Week 12 in the average number of urgency episodes (urgency: need to urinate immediately) per day

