7.2. Subject Discontinuation/Withdrawal from the Study

- Subjects who discontinue study drug will also withdraw from the study.
- A subject may choose to withdraw from the study at any time at his own request, or may be withdrawn at any time at the discretion of the investigator for safety, behavioral, compliance, or administrative reasons.
- If a subject withdraws consent for disclosure of future information, the Sponsor or designee may retain and continue to use any data collected before such a withdrawal of consent.
- If a subject withdraws from the study, he may request destruction of any blood or urine samples taken and not tested, and the investigator must document this in the site study records.
- Subjects who withdraw from the study will not be replaced (enrollment accounts for a predetermined dropout rate).

The Week 24/Early Withdrawal assessments will be completed when a subject withdraws or is withdrawn from the study, if possible (see Schedule of Assessments in [Section 1.3](#) and [Section 1.4](#)).

Reasons for discontinuation from the study include the following:

- AE
- Lack of efficacy
- Noncompliance
- Withdrawal of consent
- Lost to follow-up
- Physician decision
- Protocol deviation
- Death
- Screen failure
- Run-in Failure
- Other

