4.2.2. Reporting Conventions

General rules

In general, all collected safety data and any derived efficacy and patient reported outcome (PRO) data will be presented in subject data listings for all enrolled subjects. Listings will be ordered by treatment group, subject number, and assessment week or event date. The treatment group presented in listings will be based on the planned assignment, unless otherwise noted.

Summary tables will be provided for all randomized subjects. Unless otherwise specified, all demographic and baseline data will be presented by treatment arm and overall. Efficacy, PRO and safety data will be presented by treatment arm. In general, continuous variables will be summarized to indicate the population sample size (N), number of subjects with available data (n), arithmetic mean, SD, median, minimum, Q1, Q3 and maximum values. Categorical variables will be summarized by the population size (N), number of subjects with available data (n), number of subjects in each category, and the percentage of subjects in each category. Unless otherwise noted, the denominator to determine the percentage of subjects in each category will be based on the number of subjects with available data (n) in the analysis set of interest. Select ordinal data may be summarized using both descriptive statistics and counts and percentages of subjects in each category, as appropriate.

For selected continuous safety endpoints, least squares means and 95% CIs will be derived from an analysis of covariance (ANCOVA) model with restricted maximum likelihood estimation. All models will include the baseline value of the parameter and any additional covariates will be noted; separate models will be fit for each timepoint. Example SAS code of a change from baseline at Week 12 is provided below:

```
proc mixed data = datain method = reml;
  class TRTA;
  model CHG = TRTA BASE / solution;
  where avisit = "Week 12";
  lsmeans TRTA / pdiff cl alpha=0.05;
run;
```

In the above code, CHG represents change from baseline, TRTA is the actual treatment received, and BASE is baseline value of the parameter.

The data analyses will be conducted using the SAS® System (SAS Institute Inc., Cary, NC) version 9.4 or above. The eClinical Solutions standard operating procedures will be followed for the creation and validation of all SAS programs and outputs.

Formats

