4.2.3. Premature Withdrawal and Missing Data

All data collected in the study database after the subject’s cessation of study treatment should be included in summary and analysis. Data of subjects who withdraw after the screening examination or are not treated will only be listed. Assessments taken after the End of Study visit date for subjects continuing on to study URO-901-3006 will not be included in analysis or listings for study URO-901-3005; it will be included in datasets to support inclusion in analysis of study URO-901-3006.

If any visits are missing diary data, no explicit missing data imputation will be performed for the primary analysis of change from baseline since a mixed model for repeated measures (MMRM) will be applied to change from baseline analysis. If time to bed or time to awaken the next morning is missing from a diary day, the average of non-missing days for that subject at that visit

will be used. If no visit average bedtime or time of awakening is calculable, no nocturia measurements will be calculated for that subject at that visit.

Missing items from the subject reported outcomes (PROs) will be handled according to the respective measure instructions as described in Section 4.3.2.

Missing return dates from the study drug log will be imputed as the day of the subsequent drug dispensation, end of treatment visit, or subject discontinuation in the study, whichever is first. Non-return of IP will be considered taken per protocol for calculation of treatment compliance but will be noted in the listing of study medication.

If the first dose of double-blind study medication is not witnessed, the start of medication will be imputed as the day after the drug was dispensed.

In general, missing safety data will not be imputed and only observed values will be analyzed.

If the relationship of an AE record (“Relationship to investigational product” on AE CRF) is missing this AE will be considered “Probably Related” to the study treatment. If the AE intensity is missing every effort should be made to acquire the information from the investigator. “Severe” will be assigned to a missing intensity for reporting purposes.

The general imputation rules of partial missing date and time for both AE and concomitant medication is detailed below:

Dates missing the day of the year will adhere to the following conventions:

- The missing day of onset date will be set to:

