visit. The average of triplicates will be used for summary; if fewer than three measurements were collected the average of available measurements will be used. For subjects in Study Part 1 and visits with orthostatic blood pressure assessments, blood pressure (in triplicate) and pulse rate taken pre-dose in sitting position are equivalent to pre-dose regular vital sign values and will be used.

Vital signs will be summarized using absolute value and change from baseline. A summary by-visit according to the visit window rule in [Section 4.2.4.2](#), the maximum, and last post-baseline observation for each subject will be summarized for each of the vital signs. For change from baseline in blood pressure and pulse rate, least squares mean estimates and 95% CIs as described in section 4.2.2 will be presented from an ANCOVA model including terms for treatment, age, baseline parameter value, and pre-existing hypertension (Yes vs. No).

The line plot of mean (SE) of change from baseline in blood pressure and pulse rate over time will be prepared. A by-subject listing, sorted by subject identifier, will be presented including all vital sign results (scheduled or unscheduled).

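### SAP 7.5 analyses PVR visit by visit on observed cases although a PVR of 300 mL or more ends participation; later differences would be understated if more vibegron than placebo men cross that value

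*SAP*

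**What the plan says.** SAP 7.5 provides that "PVR urine volume data will be summarized at Baseline and every visit, including change from baseline for post-baseline visits". LS means and 95% CIs "will be presented from an ANCOVA model including terms for treatment and baseline parameter value", and the LS-mean changes are plotted by visit. The model is the one in SAP 4.2.2, where "separate models will be fit for each timepoint". On missing data, SAP 4.2.3 says: "In general, missing safety data will not be imputed and only observed values will be analyzed". SAP 7.5 also asks for a categorical summary with a top category of 300 mL or more, and a listing of all PVR data.

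Protocol 2.4.2 says that "subjects with a single PVR volume of ≥ 300 mL or an AE of urinary retention will be withdrawn", and protocol 7.1 lists the same two events as reasons for stopping study drug. Protocol 7.2 adds: "Subjects who discontinue study drug will also withdraw from the study".

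SAP 4.2.4.2 keeps the triggering value. If several on-treatment safety values fall in one window, the worst is used. An early-withdrawal assessment counts if it falls in a visit window and within 21 days of the last dose.

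**The concern.** Whether a man has a PVR at later visits depends on a PVR already recorded for him. A model for a later visit that adjusts only for baseline cannot use that recorded value. Inclusion criterion 11 requires a baseline PVR below 100 mL, so every man removed by the 300 mL rule has risen by more than 200 mL.

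The protocol treats urinary retention as a safety need particular to this population and says PVR will be closely monitored. The by-visit LS means and their plot are the only modelled PVR comparison. If vibegron pushes more men over 300 mL, the Week 12 and Week 24 differences would move toward no difference because those men have left.

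Other safety data get summaries that do not have this weakness. For vital signs, SAP 7.3.1 states that "the maximum, and last post-baseline observation for each subject will be summarized for each of the vital signs". The laboratory shift tables in SAP 7.2 use maximum, minimum and last values. The urodynamics section, SAP 7.6, reports values at any time post-baseline. SAP 7.5 names none of these for PVR.

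**Working it through.** The documents give no PVR effect, SD, margin or rate of crossing 300 mL, so there is no planned figure to reproduce. All rates and distributions below are assumptions.

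**Closed form.** Let pV and pP be the shares of each arm already withdrawn for PVR of 300 mL or more before a given visit. Let E be the mean PVR excess of those men over men who stayed, taken as equal in both arms. The complete-data arm mean is the stayers' mean plus p × E; the observed-case mean is the stayers' mean alone. So:

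understatement = E × (pV − pP)

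| Withdrawn, vibegron / placebo | E = 200 mL | E = 400 mL |
|---|---|---|
| 1% / 1% | 0 | 0 |
| 0.5% / 0.25% | 0.5 mL | 1.0 mL |
| 1% / 0.5% | 1.0 mL | 2.0 mL |
| 2% / 1% | 2.0 mL | 4.0 mL |
| 3% / 1% | 4.0 mL | 8.0 mL |

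**Simulation A.** 544 men per arm; baseline median about 25 mL, truncated below 100 mL; six post-baseline visits; a lasting 8-fold rise from a random visit in affected men; removal after the first value of 300 mL or more; 400 replicates. Week 24 differences in mL:

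| Affected, vibegron / placebo | Complete data | Planned ANCOVA | Lost | Repeated-measures likelihood | ANCOVA on last value |
|---|---|---|---|---|---|
| 2% / 1% | 2.5 | 1.3 | 1.2 (48%) | 2.0 | 3.4 |
| 3% / 1% | 4.6 | 2.1 | 2.5 (54%) | 3.4 | 6.2 |
| 4% / 1% | 7.0 | 3.2 | 3.8 (54%) | 5.3 | 9.1 |

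A rerun with 300 replicates gave similar losses and, at 1% / 1%, no bias (−0.1 for both complete data and planned ANCOVA). If instead PVR rises 20% in all vibegron men with equal retention, little is lost (7.1 against 6.5).

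The repeated-measures likelihood recovers 0.7/1.2, 1.3/2.5 and 2.1/3.8 of the gap, or 52% to 58%. The last-value ANCOVA exceeds the complete-data difference by 30% to 36%.

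**Simulation B.** Different assumptions: log-normal PVR with median 25 mL, log-scale SD 0.8 and correlation 0.6; a lasting added rise averaging 315 mL in affected men; an optional general shift in all vibegron men; 200,000 per arm. Week 24 differences in mL:

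| Ever 300 mL or more, vibegron / placebo | General shift | Complete data | Observed-case | Lost |
|---|---|---|---|---|
| 0.66% / 0.65% | none | 0.01 | 0.02 | none |
| 0.76% / 0.64% | 10% | 3.05 | 3.00 | 0.05 (2%) |
| 1.22% / 0.66% | 10% | 4.71 | 3.49 | 1.22 (26%) |
| 1.68% / 0.67% | 10% | 6.48 | 4.09 | 2.39 (37%) |
| 2.50% / 0.67% | 30% | 14.42 | 10.63 | 3.79 (26%) |
| 2.06% / 1.10% | none | 3.23 | 0.78 | 2.45 (76%) |
| 0.73% / 1.09% | 10% | 1.55 | 2.67 | −1.12 (overstated) |

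The first post-baseline visit was unaffected in every run. The proportional loss is largest when the whole effect sits in the few men who cross, as in the 76% row.

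**The case against.** **Direction.** A reader might infer that the plan does understate a vibegron effect on PVR. The documents do not support that. It requires a higher crossing rate on vibegron, which they do not give, and protocol 2.3.1 reports no notable mean PVR change in an earlier Phase 3 study. This objection stands, so the point must be conditional. The condition is, however, the harm that PVR is monitored to detect.

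**Who is left.** A reader might also infer that Week 12 and Week 24 compare only men who never reached 300 mL. That is too strong. A man who first crosses at Week 12 is in the Week 12 model, and an early-withdrawal value can fall in a later window.

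**Other displays.** The 300 mL category, the listing, the retention AESI and the discontinuation summaries keep some of these events visible, arguably more directly than a mean of a skewed variable. This stands in part, with four limits:

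- Protocol 8.4.6 records a retention AE only if catheterisation is also needed, so a man at 300 mL without it is withdrawn but is not a retention case.
- The discontinuation reasons in protocol 7.2 have no PVR entry.
- SAP 7.5 does not say that the categorical summary has an any-time row. Under SAP 4.2.2 the default denominator is men with available data, so in a by-visit table withdrawn men leave numerator and denominator together.
- A listing is not a comparison by arm.

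**Size and target.** The losses are a few mL against category limits of 100, 200 and 300 mL, and PVR has no formal hypothesis or margin, so no test is invalidated. The complete-data Week 24 value is also hypothetical, since it supposes men stayed after the withdrawal trigger, and no document defines that target. Both points stand.

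**Replacing the model.** Per-visit ANCOVA is the SAP's convention for selected safety endpoints, including blood pressure and pulse. The repeated-measures alternative recovers only part of the loss. This stands against replacement, but not against additions.

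**Conclusion.** The point holds in conditional form. The planned PVR model leaves a recorded, withdrawal-triggering value out of all later visits' comparisons. If more vibegron than placebo men cross 300 mL, later LS-mean differences and the plot would be too small; with equal rates there is no bias, and with more placebo crossings they would be too large.

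Under the assumed rates the closed form gives 0.5 to 8 mL. The simulations with an excess of affected vibegron men give 1.2 to 3.8 mL, about a quarter to a half of the difference in most cases and three-quarters in one with no general shift. These sizes rest entirely on assumed crossing rates and on a lasting rise in the affected men.

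The firmer gap is in reporting: no maximum, last or any-time PVR comparison by arm is specified, although the SAP gives comparable summaries for vital signs, laboratory values and urodynamics. It is worth correcting because it is cheap, not because the per-visit ANCOVA is invalid as an observed-case display.

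**What to change.** Keep the per-visit ANCOVA and its plot in SAP 7.5, labelled observed-case, and add:

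1. By arm in the SAF, maximum and last post-baseline PVR and the proportion of men with any post-baseline PVR of 300 mL or more. This follows SAP 7.3.1 and uses the any-time and maximum conventions already in SAP 4.2.2.
2. As a sensitivity analysis, an MMRM for change in PVR over the visits scheduled in both parts (Weeks 2, 4, 8, 12, 20 and 24), with treatment, visit, treatment-by-visit, baseline PVR and baseline-by-visit terms and an unstructured covariance. Weeks 1 and 16 are left out because the current Part 2 schedule has no PVR at those remote visits.

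The cost is SAP wording, a few output entries and code of the kind SAP 6.1.1 already specifies. No new data are needed and no change to the withdrawal rule is proposed. There are two limits to state alongside the results. PVR is skewed, so the MMRM is approximate and recovers only part of the loss (about half in simulation A). The last-value summary mixes follow-up times and can overshoot the Week 24 difference.

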1.2.2. Randomization and Blinding

Randomization will occur centrally using an interactive web response system (IWRS) using central, stratified block randomization. Randomization will be stratified based on the following stratification factors:

- Baseline average micturition episodes per day (≤ 12 vs > 12), and
- Alpha blocker use with or without 5-ARI (with vs without), and
- Urinary Incontinence (yes vs no)

Part 1 and Part 2 excluding the urodynamics sub-study will use the same stratified block randomization list. In order to ensure balanced treatment assignment within the urodynamics sub-study a separate randomization list with the same stratification factors and the block size will be used for subjects enrolled in the sub-study.

For this study in the double-blind treatment phase a double-blind/masking technique will be used: vibegron and its matching placebo will be packaged identically so that treatment blind/masking is maintained. The patient, the Investigator, and Sponsor personnel or delegate(s) who are involved in the treatment or clinical evaluation of the patients will not be aware of the treatment group assignments.

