1.2.4.2. Urodynamics Substudy

Approximately 75 subjects will be enrolled in the Urodynamics substudy, randomized 1:1 to placebo or vibegron 75mg. Assuming a 20% drop-out rate, 60 subjects will be evaluable, 30 in each treatment arm. Noninferiority margins of -3 mL/second for maximum urinary flow (Qmax) and 15 cm H₂O for detrusor pressure at maximum urinary flow (PdetQmax) from Abrams et al [1] were used to characterize power. Standard Deviation of each parameter was estimated from Nitti et al [2], which used the same noninferiority margins.

Using the noninferiority margins described above and a one-sided test of noninferiority with type-I error of 0.05:

30 evaluable subjects per treatment group provides approximately 97% power against the alternative hypothesis of equality for Qmax assuming standard deviation of 3.2 mL/second.

For PdetQmax, 30 evaluable subjects per treatment group provides approximately 79% power against the alternative hypothesis of equality assuming standard deviation of 23.5 cm H₂O. Assuming independence of these tests and requiring both to be within the non-inferiority margin, the power of the composite outcome is approximately 77%.

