6.1. Co-Primary Endpoint Analysis

6.1.1. Primary Analysis

The primary analysis will be based on the FAS. Descriptive summary for observed and CFB will be provided by visit and treatment for both co-primary endpoints. Refer to parameter derivations from Bladder Diary data on Section 4.3.1.

Co-primary 1: CFB to Week 12 in average number of daily micturition episodes

For the assessment of difference between the treatment groups in change from baseline to Week 12 in average number of daily micturition episodes, a mixed model for repeated measures (MMRM) will be used incorporating on-treatment values at all time points (Weeks 2, 4, 8, 12, 16, 20, and 24). The model takes account of any correlation within the same subject over time by using all available data on the subjects. With the assumption of missing at random (MAR), this approach will provide unbiased estimates of treatment effects derived from the model.

The MMRM model will include terms for treatment, visit, baseline value (average number of daily micturition episodes), alpha blocker use with or without 5-ARI (with vs. without), baseline urinary incontinence (yes vs. no), region (US vs. non-US), and interaction of visit by treatment. Stratification factors as randomized will be used in the model. The Kenward-Roger adjustment will be used with restricted (or residual) maximum likelihood (REML) to make statistical inference. An unstructured covariance matrix will be used to model the correlation among repeated measurements. If the unstructured covariance model fails to converge with the default Newton-Raphson algorithm, the Fisher scoring algorithm will be used to provide initial values of the covariance parameters. In the rare event that none of the above methods yield convergence, the following structures will be investigated: heterogeneous Toeplitz, Toeplitz, heterogeneous First-Order Autoregressive [AR (1)], heterogeneous compound symmetry (HCS), and compound symmetry (CS). The covariance structure converging to the best fit, as determined by Akaike's information criterion (AIC), will be used.

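### The PVR, uroflow and urodynamics ANCOVAs omit the stratification factors, so their intervals will be somewhat conservative if those factors predict outcome beyond baseline

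*SAP*

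**What the plan says.** SAP 7.5 (PVR), 7.6 (urodynamics) and 7.7 (uroflow) use the same phrase: least squares means and 95% CIs are "presented from an ANCOVA model including terms for treatment and baseline parameter value". The general rule for safety models is in SAP 4.2.2: "All models will include the baseline value of the parameter and any additional covariates will be noted". Sections 7.5 to 7.7 note none, and the example code in 4.2.2 has only treatment and baseline on the right-hand side.

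SAP 1.2.2 stratifies randomisation on three two-level factors: baseline micturitions per day (split at 12), alpha blocker with or without a 5-ARI, and urinary incontinence. For the urodynamics sub-study, "a separate randomization list with the same stratification factors and the block size will be used for subjects enrolled in the sub-study".

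The efficacy analyses largely carry these factors. SAP 6.1.1 says of the micturition model: "Stratification factors as randomized will be used in the model". That model has the 5-ARI and incontinence factors, with continuous baseline micturitions in place of the split at 12. The urgency model has all three. The multiple-imputation ANCOVA (SAP 6.1.2.2) follows the same pattern, and the urgency responder analysis (SAP 6.3.1) is stratified on all three.

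SAP 1.2.4.2 sizes the sub-study: "Assuming a 20% drop-out rate, 60 subjects will be evaluable, 30 in each treatment arm". It gives margins and power for Qmax and PdetQmax, which SAP 3.1.7 calls the primary urodynamics parameters. SAP 7.6 provides one-sided 95% CIs for both.

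**The concern.** Stratified randomisation balances the arms on the chosen factors. If a factor predicts the outcome and is left out of the model, its variance stays in the error term although it contributes little to the true sampling variation of the treatment difference. The standard error is then too large and the interval conservative.

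BPH regimen and incontinence status could plausibly relate to residual volume, flow and detrusor pressure, although the documents give no evidence either way. The parameter's own baseline is already in the model and may absorb much of that. It may absorb less where the baseline is old: a urodynamic trace may date from up to 6 months before screening (Protocol 8.3.7), and uroflow compares Screening with Week 24 (SAP 7.7).

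At stake is some precision in the PVR and uroflow estimates, and in the bounds for the only two parameters in the SAP that have non-inferiority margins.

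**Working it through.** **Inputs from SAP 1.2.4.2.** 30 evaluable per arm; one-sided alpha 0.05; Qmax margin 3 mL/s in size, SD 3.2; PdetQmax margin 15 cmH2O, SD 23.5; stated power 97%, 79% and 77% jointly.

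**Assumed.** R² is the share of the variance left after treatment and baseline that the three factors jointly explain. The documents do not give it; the range 0 to 0.20 is shown. The SAP's SDs are used as the residual SDs of the planned model.

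**Step 1: reproduce the stated power.** Power = Φ(margin / (SD × √(2/30)) − 1.645).

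- Qmax: SE = 3.2 × 0.2582 = 0.826; 3/0.826 − 1.645 = 1.986; power 97.6%.
- PdetQmax: SE = 23.5 × 0.2582 = 6.068; 15/6.068 − 1.645 = 0.827; power 79.6%.
- Joint, assuming independence as the SAP does: 0.976 × 0.796 = 77.7%; the product of the stated values is 0.97 × 0.79 = 76.6%.
- A noncentral t calculation on 58 df gives 97.4% and 78.8%.
- Enrolment: 60 / (1 − 0.20) = 75.

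The stated figures reproduce and take no credit for baseline or the stratification factors.

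**Step 2: effect of adding three main effects with 60 men.** Half-width ratio = √(1 − R²) × t(54 df) / t(57 df). The one-sided 95% critical values are 1.674 and 1.672. The planned half-widths are 1.672 × 0.826 = 1.38 mL/s and 1.672 × 6.068 = 10.15 cmH2O. Joint power below is from the noncentral t on 54 df.

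| Assumed R² | Half-width ratio | Qmax half-width | PdetQmax half-width | Joint power |
|---|---|---|---|---|
| 0 | 1.001 | 1.38 | 10.16 | 76.6% |
| 0.05 | 0.976 | 1.35 | 9.90 | 78.8% |
| 0.10 | 0.950 | 1.31 | 9.63 | 81.0% |
| 0.20 | 0.895 | 1.24 | 9.08 | 85.3% |

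By the normal approximation of Step 1, PdetQmax at R² = 0.05 has SE = 6.068 × √0.95 = 5.914; 15/5.914 − 1.645 = 0.891; power about 81%, against 79.6%.

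**Step 3: the main study.** With about 924 men the degrees of freedom no longer matter. The ratio is 1.000, 0.990, 0.975 and 0.949 at R² = 0, 0.02, 0.05 and 0.10. With 800 men it is the same to three decimals.

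**Step 4: simulation check.** Stratified permuted blocks over 8 strata were simulated, with an assumed block size of 4, assumed factor prevalences of 50%, 50% and 30%, and two-sided 95% intervals. With 60 men the half-width ratio was 1.005, 0.980, 0.952 and 0.899 at R² = 0, 0.05, 0.10 and 0.20. Coverage of the planned interval was 0.956 to 0.966 with 60 men and 0.947 to 0.967 with 924: nominal to conservative.

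**The case against.** The strongest reply is that nothing here is invalid. The gain depends on an R² that the documents do not supply; at R² = 0 there is none, and the sub-study loses slightly. The stated power is reached without the factors. PVR and uroflow have no hypothesis, margin or power statement, and Protocol 9.4.3.4 plans only descriptive statistics for urodynamics. SAP 7.6 provides one-sided CIs without a decision rule.

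The SAP also chooses covariates endpoint by endpoint. The blood pressure model in 7.3.1 adds age and pre-existing hypertension but no stratification factor. The efficacy models are not uniform either: the micturition model drops the split at 12, and the urge incontinence model drops incontinence status. Finally, two urodynamic parameters exist only if an involuntary detrusor contraction (IDC) occurs, so three extra terms would cost more there.

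Most of this stands, and it sets the size of the point. It does not explain the omission. Where the micturition and urge incontinence models drop a factor, there is a visible reason: continuous baseline replaces it, or the analysis set is already restricted to incontinent men. No such reason applies to 7.5 to 7.7. The objection about the IDC parameters is met by leaving them out of the change.

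A reader might infer that the planned intervals are wider than the design allows. The documents do not support that: the design's stated precision is met, and whether the intervals are wider at all depends on the unknown R².

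**Conclusion.** The omission is real and unexplained, and its consequence is conditional. If the stratification factors are prognostic beyond baseline, the planned intervals are conservative, and adjustment would narrow them by about 2.5%, 5% or 10.5% at R² of 0.05, 0.10 or 0.20. If they are not, nothing is lost by the planned model. The percentages rest on the assumed R²; the absolute sub-study figures rest also on the SAP's SDs and 30 men per arm.

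A reader might go further and infer bias, or a non-inferiority reading tilted in the drug's favour. Neither follows. The treatment estimates are unbiased under either model, and wider bounds make non-inferiority harder to show. For PVR and uroflow the effect is a less precise estimate of any harm. The point ranks as a cheap improvement.

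**What to change.** In SAP 4.2.2, 7.5, 7.6 and 7.7, add the three stratification factors as randomised to the ANCOVA for PVR, uroflow, and sub-study Qmax and PdetQmax, for example `model CHG = TRTA BASE MICTSTRAT ALPHAB UI`, with the three factors also in the class statement. Enter them as main effects (3 df), not as the 8 stratum cells, which would be sparse with 60 men. Keep the planned model for the two parameters measured only if an IDC occurs. If the team prefers the planned model throughout, state the reason and pre-specify the adjusted model as a sensitivity analysis before unblinding.

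The cost is a short change to the SAP text and the analysis code, plus 3 degrees of freedom. If the factors predict nothing, intervals in the 60-man sub-study widen by about 0.1% (formula) to 0.5% (simulation), with no measurable change at about 924.
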